7.6 Handling of Bio specimens Collected for Correlative Research

Bio specimens collected for this study will be stored in the Lineberger Comprehensive Cancer Center (LCCC) Tissue Procurement Facility (TPF), or, if needed, in a secure off-site storage facility. All bio specimens will be obtained in accordance with procedures outlined in the LCCC 1729 Study Laboratory Manual and stored in containers with controlled access. Each sample will be assigned a unique code number and no identifiable personal health information (PHI) will be on the specimen label. Information about the patient's disease will be linked to the specimens stored in the repository database. TPF-associated research staff, LCCC Bioinformatics staff who support the TPF database and the LCCC Data Warehouse, and researchers with IRB-approval for access to PHI for each subject in this study will be able to link specimens to relevant medical information. Some results from laboratory analyses that occurred during the patient's participation in the clinical study may also be included. This information may be important for understanding how the patient's cancer developed and responded to treatment.

Storage Time:

1. The biospecimen will be used first and foremost for research purposes outlined within the confines of this protocol. Samples will be discarded/destroyed after relevant data are collected for this study, unless consent was obtained from the patient to use tissue for other research purposes (e.g., TPF consent form was signed by the patient). In this circumstance, there is no time limit on how long biospecimens may be stored.
2. The Principal Investigator must agree to abide by policies and procedures of the TPF facility and sign a letter of research agreement for ethical and appropriate conduct of their research that utilizes specimens obtained from the TPF facility (e.g., use of leftover specimens will require a protocol outlining the research plan for biospecimen use).

Compliance Statement

Biospecimen collection for this study will be conducted in full accordance to all applicable University of North Carolina at Chapel Hill (UNC-CH) Research Policies and Procedures and all applicable Federal and state laws and regulations including 45 CFR 46, and the Health Insurance Portability and Accountability Act (HIPAA) Privacy Rule. Any episode of noncompliance will be documented.

The investigators will perform the study in accordance with this protocol, will obtain consent and assent (unless a waiver is granted), and will report unexpected problems in accordance with the UNC-CH IRB Policies and Procedures and all federal requirements. Collection, recording, and reporting of data will be accurate and will ensure the privacy, health, and welfare of research subjects during and after the study.

7.7 Assessment of Safety

Any patient who receives at least one dose of entinostat will be evaluable for toxicity. Each patient will be assessed periodically for the development of any toxicity according to the Time and Events table. Toxicity will be assessed according to the NCI CTCAEv5.0.

7.8 Assessment of Efficacy

7.8.1 Assessment of Disease-Tumor Measurement Based on RECIST v1.1

See the international criteria proposed by the Response Evaluation Criteria in Solid Tumors (RECIST) Committee, version 1.1 for additional details and clarifications^{149,150}.

Measurable disease will be defined as the presence of at least one measurable lesion that can be accurately measured in at least one dimension with the longest diameter a minimum size of:

- ≥ 10 mm by CT scan (CT scan slice thickness no greater than 5 mm)
- 10 mm caliper measurement by clinical exam (lesions which cannot be accurately measured with calipers should be recorded as non-measurable).
- 20 mm by chest x-ray.

For malignant-appearing lymph nodes on radiographic imaging that can be considered pathologically enlarged and measurable a lymph node must be ≥ 15 mm in short axis when assessed by CT scan with IV contrast performed with slice thickness ≤ 5 mm). At baseline and in follow-up, only the short axis will be measured and followed.

All other lesions, including small lesions (longest diameter < 10 mm or pathological lymph nodes with ≥ 10 to < 15 mm short axis) as well as truly non-measurable lesions, will be considered non-measurable. Lesions considered truly non-measurable include: leptomeningeal disease; ascites; pleural/pericardial effusion; inflammatory breast disease; lymphangitic involvement of skin or lung, abdominal masses/abdominal organomegaly identified by physical exam that is not measurable by reproducible imaging techniques.

All measurements should be recorded in metric notation, using calipers, if clinically assessed. All baseline evaluations should be performed as close as possible to the treatment start and never more than 21-days before the beginning of the treatment. The same method of assessment and the same technique should be used to characterize each identified and reported lesion at baseline and during follow-up. Imaging-based evaluation should always be done rather than clinical examination, unless the lesion(s) being followed cannot be imaged but are assessable by clinical exam. Clinical lesions will only be considered measurable when they are superficial and ≥ 10 mm diameter, as assessed using calipers (e.g. skin nodules). For the case of skin lesions, documentation by color photography, including a ruler to estimate the size of the lesions is recommended.

7.8.2 Baseline Documentation of Target and Non-Target Lesions

All measurable lesions up to a maximum of 5 lesions total (and a maximum of two lesions per organ) representative of all involved organs should be identified as target lesions and will be recorded and measured at baseline.

Target lesions should be selected on the basis of their size (lesions with the longer diameter), growth rate at the time of study enrollment (stable or regressing tumor lesions should be excluded, irrespective of other parameters), be representative of all involved organs, and, in addition, should be those that lend themselves to reproducible repeated measurements.

A sum of the diameters (longest for non-nodal lesions, short axis for nodal lesions) for all target lesions will be calculated and reported as the baseline sum diameters. If lymph nodes are to be included in the sum, only the short axis is added into the sum. The baseline sum diameters will be used as reference to further characterize the objective tumor response of the measurable dimension of the disease.

All other lesions (or sites of disease), including pathological lymph nodes, should be identified as non-target lesions and should also be recorded at baseline. Measurements are not required and these lesions should be followed as “present” or “absent”, or in rare cases “unequivocal progression”.

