4.1 Inclusion Criteria

- 4.1.1 Age \geq 18 years at the time of consent.
- 4.1.2 Subject has provided informed consent and HIPAA prior to initiation of any study-specific activities/procedures.
- 4.1.3 ECOG Performance Status of ≤ 2 .
- 4.1.4 Histologically confirmed metastatic (regional or distant) melanoma of any subtype (cutaneous, mucosal, ocular).
- 4.1.5 AJCC stage unresectable III or stage IV disease that is measurable by RECIST v1.1 criteria.
- 4.1.6 Must agree to undergo one on-treatment tumor biopsy on day 22 (± 2 days) of the study. Subjects for whom fresh samples cannot be safely provided (e.g., inaccessible tumor for biopsy) will not be eligible for study participation.
- 4.1.7 Must have available archival tissue and subjects must have consented to allow collection of archived tumor blocks from previous surgeries confirming or treating unresectable stage III or distant metastatic disease. If more than one archived tumor block is available, only one block is required to be analyzed for the presence of TIL/TALS. Archived tumor tissues must fulfill the following criteria based on two representative H&E-stained tissue sections: (1) the tumor surface area must be at least 1cm^2 (which can be from a combination of metastatic blocks if necessary), (2) no more than 20% of necrosis, (3) the ratio of viable tumor cells to tumor-associated stroma should be at least 60/40, and (4) if TILs are present based on H&E stained

sections, they must be $\leq 1\%$ of the total number of cells in the specimen; the amount of tissue should be ≥ 1 cm².

[name], study pathologist, must sign off on the eligibility of archived tumor blocks before study enrollment. If archival tissue is unavailable or insufficient, fresh biopsy should be performed to confirm unresectable stage III or distant metastatic disease.

4.1.8 Previous treatment with immune checkpoint inhibitors and chemotherapies is allowed on condition that the last treatment is at least 28 days prior to first dose of entinostat. Previous treatment with targeted therapies (e.g. MAPK inhibitors) is allowed on condition that the last treatment was administered at least 15 days prior to first dose of entinostat).

4.1.9 Demonstrate adequate organ function as defined in the table below; all screening labs to be obtained within 21 days prior to entinostat treatment.

System	Laboratory Value
Hematological*	

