6.3.6 Disease Assessment

This following test should be performed for assessment of melanoma disease.

6.3.6.1 Computed tomography (CT) of the whole body i.e., neck (if applicable), chest, abdomen, pelvis with IV contrast (or abdominal/pelvis MRI if allergy to IV contrast)

Baseline (screening) disease assessment should be obtained within 21 days of initiating study treatment. During the study, scans will be repeated as outlined in the Time and Events table in section 7.1 (i.e., at the end of week 10[D1 of cycle 4 or Study day 64/Wk10], end of week 15 [D1 of cycle 6 i.e., Study day 106/Wk16], end of week 21 [D1 of cycle 8 or Study day 148/Wk22], and end of week 27). Scans obtained during study treatment may be performed within ± 7 days of the scheduled study visit.

6.3.6.2 *Magnetic Resonance Imaging (MRI) of the brain*

MRI of the brain must be obtained at baseline (screening) and at end of treatment (i.e., at time of disease progression or at week 27); on any other visit **only if clinically indicated**, as per standard of care. If brain MRI is not feasible, patient can have a CT scan with IV contrast.

6.3.7 **Pre-Screening Pathology Assessment Period (pre-screening only)**

Given the limited 21-day screening period, and the requirement for absent TIL/TAL in melanoma tissues, archival metastatic tissue (locoregional, distant metastatic) can be requested and assessed before study enrollment (pre-screening). There is not an official pre-screening period given that [name], study's pathologist, is UNC's sole melanoma pathologist and routinely signs off his pathology reports, either from outside consultation slides or from in-house cases, along with a report about the presence of absence of tumor-infiltrating/-associated lymphocytes. If not available already, representative tumor sections from archived tumor blocks will be stained with H&E and will be assessed by [name], study pathologist, for assessment of quality using these criteria: (1) the tumor surface area must be at least 1cm² (which can be from a combination of metastatic blocks if necessary), (2) no more than 20% of necrosis, (3) the ratio of viable tumor cells to tumor-associated stroma should be at least 60/40, and (4) if TILs are present based on H&E stained sections, they must be $\leq 1\%$ of the total number of cells in the specimen; the amount of tissue should be ≥ 1 cm².

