7.8.3 Evaluation of Target Lesions using RECIST 1.1 Criteria

NOTE: In addition to the information below, also see section 4.3.2 in the international criteria proposed by the Response Evaluation Criteria in Solid Tumors (RECIST) Committee, version 1.1¹⁵⁰ for special notes on the assessment of target lesions.

Complete response (CR) – Disappearance of all target lesions. Any pathological lymph node (whether target or non-target) must have decreased in short axis to <10 mm.

Partial response (PR) – At least a 30% decrease in the sum of the LD of the target lesions taking as reference the baseline sum LD.

Progressive Disease (PD) – At least a 20% increase in the sum of the LD of the target lesions taking as reference the smallest sum LD recorded since the treatment started including baseline if that is the smallest on study. In addition to the relative increase of 20%, the sum must also demonstrate an absolute increase of at least 5 mm. The appearance of one or more new lesions also constitutes PD.

Stable disease (SD) – Neither sufficient shrinkage to qualify for PR nor sufficient increase to qualify for PD taking as references the smallest sum LD since the treatment started.

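### Section 7.8.2 gives two target-lesion rules that cannot both be followed, and the choice between them can move the same scans between SD and PR or PD

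*Combined protocol and SAP*

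**What the plan says.** The first paragraph of section 7.8.2 makes target lesions of "All measurable lesions up to a maximum of 5 lesions total (and a maximum of two lesions per organ) representative of all involved organs". The second paragraph lists what selection rests on: size, growth rate at enrolment, organ representation and reproducibility. Attached to growth rate is the instruction that "stable or regressing tumor lesions should be excluded, irrespective of other parameters". Every lesion not chosen becomes non-target. It needs no measurement and is followed qualitatively, with unequivocal progression as the rare exception.

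Section 7.8.3 builds response on the target sum. PR is "At least a 30% decrease in the sum of the LD of the target lesions taking as reference the baseline sum LD". PD is "At least a 20% increase in the sum of the LD of the target lesions" relative to the smallest sum on study, with an absolute increase of at least 5 mm; a new lesion is also PD.

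Eligibility (4.1.5) asks for "disease that is measurable by RECIST v1.1 criteria" and does not ask that any lesion be growing. On imaging, section 6.3.6 says "Baseline (screening) disease assessment should be obtained within 21 days of initiating study treatment" and requires no earlier comparison scan. Sections 3.2.1 and 3.2.2 define week-10 ORR and 27-week PFS by RECIST v1.1.

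**The concern.** Three problems follow from reading these sections together.

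- **Conflict.** When a patient's measurable lesions fit within the caps, the first paragraph takes in all of them and the second removes any that are stable or regressing. If an organ's only measurable lesion is stable, the exclusion also defeats the aim of representing every involved organ.
- **No way to apply the exclusion consistently.** Stable and regressing are not defined. One baseline scan cannot show growth, so the judgement depends on whatever pre-study imaging exists.
- **Empty target list.** A patient whose measurable lesions are all stable or regressing meets 4.1.5 but has no target lesion, so there is no sum on which to assign PR or the 20% progression rule.

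Two assessors could therefore draw up different target lists from the same baseline scan and reach different response categories. Because excluded lesions need not be measured, the full sum may not be recoverable from the recorded data. Progression also ends study therapy (5.2, 5.8), so the ambiguity reaches conduct as well as reporting.

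**Working it through.** **The plan's own figure.** Section 9.2 gives exact 95% intervals for the response rate with 10 patients. Clopper-Pearson limits are 0 to 0.3085 for 0/10 (upper limit 1 - 0.025^(1/10)) and 0.0025 to 0.4450 for 1/10. These agree with the stated (0, 0.31) and (0, 0.45).

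**Inputs.** The thresholds are those of 7.8.3: PR at -30% or lower from baseline; PD at +20% or higher and at least +5 mm from the smallest sum. The lesion diameters are assumptions, since the documents give none. Lesions lie in at least two organs (the cap is two per organ), the baseline sum is the smallest so far, and there is no new lesion or unequivocal non-target progression.

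**Illustration 1.** One growing lesion of 30 mm; two stable lesions of 30 and 40 mm that do not change. Baseline sum: 100 mm for all measurable lesions, 30 mm with stable lesions excluded.

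| Growing lesion | Stable lesions excluded | All measurable lesions |
|---|---|---|
| 30 to 20 mm | (20 - 30)/30 = -33%: PR | (90 - 100)/100 = -10%: SD |
| 30 to 37 mm | (37 - 30)/30 = +23%, +7 mm: PD | (107 - 100)/100 = +7%: SD |

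**Illustration 2, opposite direction.** Two growing lesions of 30 and 20 mm stay unchanged, and one regressing lesion goes from 50 to 18 mm. All measurable: (68 - 100)/100 = -32%, PR. Regressing lesion excluded: (50 - 50)/50 = 0%, SD.

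**General form.** Let s be the share of the full baseline sum in lesions that stay unchanged. Under the all-measurable rule the remaining lesions must shrink by 30%/(1 - s) for PR or grow by 20%/(1 - s) for PD. With the unchanged lesions excluded, the thresholds stay at 30% and 20%.

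| s | Shrinkage needed for PR | Growth needed for PD |
|---|---|---|
| 10% | 33.3% | 22.2% |
| 20% | 37.5% | 25.0% |
| 30% | 42.9% | 28.6% |
| 40% | 50.0% | 33.3% |
| 50% | 60.0% | 40.0% |
| 60% | 75.0% | 50.0% |

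A change that falls between the two thresholds is SD under one rule and PR or PD under the other. Illustration 1 has s = 70/100 = 70%, which is beyond the table. At smaller s the band is narrower but still present.

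**Effect on ORR.** Section 9.2 expects a response rate close to zero. One reclassified patient moves 0/10 to 1/10, and the upper confidence limit from 0.31 to 0.45.

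**The case against.** The best defence is that 7.8.2 gives a general rule and then a specific one. The first paragraph sets the pool and the caps, the second says how to choose, and the override wording in the exclusion already settles precedence. Taken that way the conflict narrows. The missing definition, the missing comparison scan and the possible empty target list remain.

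The exclusion also has a plausible purpose. Entry is allowed 28 days after checkpoint inhibitors or chemotherapy and 15 days after targeted therapy (4.1.8), and 15 days after radiation or major surgery (4.1.12). A lesion still shrinking from earlier treatment could yield a PR that owes nothing to the study drugs; illustration 2 shows how. This stands, and any fix must keep that protection.

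Several further limits also stand. The text says lesions should be excluded, not that they must be. A PR counts as best overall response only if confirmed more than 4 weeks later (7.8.5). The lesion sizes are invented, and the documents do not say how often such patients will occur.

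A reader might infer that a single growing lesion would decide ORR and PFS. The documents do not support that: unequivocal progression of non-target lesions and new lesions are PD under either rule (7.8.4). A reader might also infer an upward bias in ORR through regression to the mean. Nothing in the documents quantifies it, and illustration 2 shows that the exclusion can also remove a PR.

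**Conclusion.** The point holds. The two instructions conflict at or below the caps, and even if the exclusion is taken to prevail it cannot be applied reproducibly and can leave an eligible patient with no target lesion. Under the protocol's own thresholds the choice of rule can move identical scans between SD and PR or PD, in either direction. The size shown is what is possible under assumed diameters; it is not an expected frequency or a net bias.

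The effect is confined to the secondary endpoints, week-10 ORR and 27-week PFS, which are estimated and carry no decision rule. It would be wrong to infer that the trial's main conclusion is at risk: conversion of TIL/TAL status is read on H&E sections, and its rule of 3 in 10, type I error and power do not depend on lesion selection. The passage should be corrected before response is scored, because with about 10 evaluable patients one changed category visibly alters the reported ORR.

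**What to change.** Reconcile the two paragraphs of 7.8.2 by removing the growth-rate criterion and its exclusion. Target lesions would then be all measurable lesions within the caps, chosen by size, organ representation and reproducibility where there are more than the caps allow.

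To keep the protection against carry-over, record at baseline any lesion that earlier imaging shows to be regressing, and state how that is judged. Keep measuring those lesions, and report ORR and PFS a second time with them removed from the sum. Say in advance how a patient is handled in that second analysis if no target lesion remains.

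The cost is wording plus one baseline data field. No scans or patients are added, and flagged target lesions are measured anyway. The small downside is that a lesion still shrinking from earlier therapy enters the main sum and could favour PR; the second analysis makes that visible.

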7.8.3 Evaluation of Target Lesions using RECIST 1.1 Criteria

NOTE: In addition to the information below, also see section 4.3.2 in the international criteria proposed by the Response Evaluation Criteria in Solid Tumors (RECIST) Committee, version 1.1¹⁵⁰ for special notes on the assessment of target lesions.

Complete response (CR) – Disappearance of all target lesions. Any pathological lymph node (whether target or non-target) must have decreased in short axis to <10 mm.

Partial response (PR) – At least a 30% decrease in the sum of the LD of the target lesions taking as reference the baseline sum LD.

Progressive Disease (PD) – At least a 20% increase in the sum of the LD of the target lesions taking as reference the smallest sum LD recorded since the treatment started including baseline if that is the smallest on study. In addition to the relative increase of 20%, the sum must also demonstrate an absolute increase of at least 5 mm. The appearance of one or more new lesions also constitutes PD.

Stable disease (SD) – Neither sufficient shrinkage to qualify for PR nor sufficient increase to qualify for PD taking as references the smallest sum LD since the treatment started.

7.8.4 Evaluation of Non-Target Lesions using RECIST 1.1 Criteria

Complete response (CR) – Disappearance of all non-target lesions and normalization of tumor marker levels. All LN must be non-pathological in size (<10 mm short axis).

Non-complete response (non-CR)/non-progression (non-PD) – Persistence of ≥ 1 non-target lesion(s) or/and maintenance of tumor marker level above the normal limits.

Progressive disease (PD) – Appearance of ≥ 1 new lesions and/or unequivocal progression of existing non-target lesions.

7.8.5 Evaluation of Best Overall Response using RECIST 1.1 Criteria

Please see review the RECIST v1.1 criteria for complete details¹⁵⁰. The best overall response is the best response recorded from the start of the study treatment until the end of treatment, provided the confirmation criteria are met. To be assigned a status of PR or CR, changes in tumor measurements must be confirmed by repeat studies that should be performed > 4 weeks after the criteria for response are first met. If a CR/PR cannot be confirmed, the original ‘response’ should be considered stable disease. The best overall response will be defined according to the following table:

Overall Response First Time Point	Overall Response Subsequent Time Point	BEST Overall Response
CR	CR	CR
CR	PR	SD, PD, or PR ¹
CR	SD	SD provided minimum criteria for SD duration met, otherwise, PD
CR	PD	SD provided minimum criteria for SD duration met, otherwise, PD
CR	NE ²	SD provided minimum criteria for SD duration met, otherwise, NE ²
PR	CR	PR
PR	PR	PR
PR	SD	SD
PR	PD	SD provided minimum criteria for SD duration met, otherwise, PD
PR	NE ²	SD provided minimum criteria for SD duration met, otherwise, NE ²
NE	NE ²	NE ²

¹ If a CR is truly met at first time point, then any disease seen at a subsequent time point, even disease meeting PR criteria relative to baseline, makes the disease PD at that point (since disease must have reappeared after CR). Best response would depend on whether minimum duration for SD was met. However, sometimes ‘CR’ may be claimed when subsequent scans suggest small lesions were likely still present and in fact the patient had PR, not CR at the first time point. Under these circumstances, the original CR should be changed to PR and the best response is PR.

² NE=inevaluable

